2.2.2 Preclinical and Clinical Studies

Refer to the IB for information on completed preclinical and clinical studies conducted with the 9vHPV vaccine.

2.2.2.1 Completed Clinical Studies

A global phase 3 study (Protocol V503-001) was conducted to evaluate the efficacy, immunogenicity and safety in females aged 16 to 26 years including Japanese females [Joura, E.A., et al 2015] [Huh, W.K., et al 2017] [Garland, S.M., et al 2018]. The 9vHPV vaccine prevented infection and disease caused by the HPV vaccine types and was generally well-tolerated. For younger adolescents, Protocol V503-002 was conducted and it has been demonstrated that competitive Luminex Immunoassay (cLIA) GMTs for the vaccine HPV types following 3 doses in both non-Japanese boys and girls aged 9 to 15 years were non-inferior to those in females aged 16 to 26 years, thereby supporting the bridging of efficacy findings in 16- to 26-year-old females to 9- to 15-year-old preadolescent and adolescent girls [Van Damme, P., et al 2015]. A local study (Protocol V503-008) also showed that a 3-dose regimen of the 9vHPV vaccine induced high HPV antibody responses and was generally well tolerated in Japanese girls aged 9 to 15 years [Iwata, S., et al 2017].

To investigate 2-dose regimen, a phase 3 study (Protocol V503-010) was conducted in non-Japanese boys and girls aged 9 to 14 years. The immune responses for girls and boys aged 9 to 14 years who received a 2-dose series were non-inferior to immune responses for young females aged 16 to 26 years who received a 3-dose series [Iversen, O.E., et al 2016].

Details of completed clinical studies with the 9vHPV vaccine are shown in the IB.

2.2.2.2 Ongoing Clinical Studies in Japan

A global phase 3 study (Protocol V503-049) is currently being conducted to evaluate the efficacy, immunogenicity and safety of the 9vHPV vaccine in the prevention of oral persistent infection caused by any of the high-risk HPV types covered by the vaccine in adult males 20 to 45 years of age including Japanese males.

A local phase 3 study (Protocol V503-064) is currently being conducted to evaluate the efficacy, immunogenicity and safety of the 9vHPV vaccine in Japanese males 16 to 26 years of age, in order to pursue indications for anal cancer and its precancerous or dysplastic lesions caused by vaccine 9vHPV types in both males and females, and genital warts in males in Japan.

2.3 Benefit/Risk Assessment

The 9vHPV vaccine has been shown to be beneficial and efficacious in preventing persistent genital HPV infection and disease associated with the 9 HPV types (6, 11, 16, 18, 31, 33, 45, 52, and 58). The frequency, severity, and magnitude of adverse events (AEs) identified in previous studies [Moreira, E.D.J, et al 2016] [Moreira, E.D.J, et al 2018] and post marketing

surveillance [Shimabukuro, T.T., et al 2019] [Donahue, J.G., et al 2019] support a favorable benefit-risk for the 9vHPV vaccine in this study population.

Additional details regarding specific benefits and risks for participants participating in this clinical study may be found in the accompanying IB and informed consent documents.

3 HYPOTHESES, OBJECTIVES, AND ENDPOINTS

This study will evaluate 2 different dose regimens of the 9-valent human papillomavirus (9vHPV) vaccine: a 3-dose regimen in Japanese boys aged 9 to 15 years old and a 2-dose regimen in Japanese boys and girls aged 9-14 years old. The base phase of the study (Period I) will assess the immunogenicity and safety of the 9vHPV vaccine through 7 months following the first dose. The extension phase of the study (Period II) will assess the safety and the antibody persistence to the 9vHPV vaccine through 30 months following the first dose.

Objectives	Endpoints	
Primary		
- To estimate percent seroconversion for the vaccine HPV types (6, 11, 16, 18, 31, 33, 45, 52 and 58) at Month 7 in Japanese boys aged 9 to 15 years who received 3 doses of the 9vHPV vaccine	- Serum antibody titer to each of HPV 6, 11, 16, 18, 31, 33, 45, 52 and 58	
- To estimate percent seroconversion for the vaccine HPV types (6, 11, 16, 18, 31, 33, 45, 52 and 58) at Month 7 in Japanese boys aged 9 to 14 years who received 2 doses of the 9vHPV vaccine	- Serum antibody titer to each of HPV 6, 11, 16, 18, 31, 33, 45, 52 and 58	
- To estimate percent seroconversion for the vaccine HPV types (6, 11, 16, 18, 31, 33, 45, 52 and 58) at Month 7 in Japanese girls aged 9 to 14 years who received 2 doses of the 9vHPV vaccine	- Serum antibody titer to each of HPV 6, 11, 16, 18, 31, 33, 45, 52 and 58	
- To evaluate the safety and tolerability of the 9vHPV vaccine in Japanese boys aged 9 to 15 years who received 3 doses and Japanese boys and girls aged 9 to 14 years who received 2 doses of the 9vHPV vaccine	 Solicited injection-site adverse events Systemic adverse events Serious adverse events 	

PRODUCT: V503
PROTOCOL/AMENDMENT NO.: 066-02

Objectives		Endpoints	
Secondary			
_	To estimate the immune response for the vaccine HPV types (6, 11, 16, 18, 31, 33, 45, 52 and 58) at Month 7 including geometric mean titers (GMTs) in Japanese boys aged 9 to 15 years who received 3 doses of the 9vHPV vaccine	-	Serum antibody titer to each of HPV 6, 11, 16, 18, 31, 33, 45, 52 and 58
_	To estimate the immune response for the vaccine HPV types (6, 11, 16, 18, 31, 33, 45, 52 and 58) at Month 7 including GMTs in Japanese boys aged 9 to 14 years who received 2 doses of the 9vHPV vaccine	_	Serum antibody titer to each of HPV 6, 11, 16, 18, 31, 33, 45, 52 and 58
_	To estimate the immune response for the vaccine HPV types (6, 11, 16, 18, 31, 33, 45, 52 and 58) at Month 7 including GMTs in Japanese girls aged 9 to 14 years who received 2 doses of the 9vHPV vaccine	_	Serum antibody titer to each of HPV 6, 11, 16, 18, 31, 33, 45, 52 and 58
Tertiary/Exploratory			
_	To assess the persistence of anti-HPV 6, 11, 16, 18, 31, 33, 45, 52 and 58 antibody responses at Month 18 and 30	_	Serum antibody titer to each of HPV 6, 11, 16, 18, 31, 33, 45, 52 and 58

4 STUDY DESIGN

4.1 Overall Design

V503-066-02 FINAL PROTOCOL

This is a phase 3 open-label study to evaluate the immunogenicity and safety of a 9vHPV (types 6, 11, 16, 18, 31, 33, 45, 52, and 58) vaccine (V503) in Japanese boys and girls aged 9 to 15 years. This study will consist of two periods. Period I of the study is to evaluate the immunogenicity and safety/tolerability of the 9vHPV vaccine up to the time point of Month 7. Period II of the study is to evaluate the long-term immunogenicity and safety from Month 7 to Month 30. Analysis of the base phase (Period I) for the 2-dose arm in girls aged 9 to 14 years old is planned to be conducted when all girl participants have completed their Period I (Month 7 visit) or discontinued from study before that time. Analysis of the base phase (Period I) for the 2-dose and 3-dose arms in boys and extension phase (Period II) for all arms will be conducted at the end of study.

This study will enroll approximately 300 Japanese boys and girls in total, and approximately 100 participants will be allocated to each of the following three arms:

31

- 3-dose (Day 1, Month 2 and Month 6) in boys aged 9 to 15 years
- 2-dose (Day 1 and Month 6) in boys aged 9 to 14 years
- 2-dose (Day 1 and Month 6) in girls aged 9 to 14 years

Enrollment of the girl cohort will be initiated first. Enrollment of the boy cohorts will be initiated at a later time to be determined by the Sponsor.

Blood samples will be collected on Day 1 immediately before vaccination, and subsequently Month 7, Month 18 and Month 30 to evaluate HPV antibody responses.

Participants will be followed for injection-site AEs and systemic AEs from Day 1 through Day 15 following each vaccination. SAEs will be recorded regardless of causality from the time of allocation/randomization through 6 months post last dose. Vaccine-related SAEs and deaths will be collected throughout the study. New medical conditions (defined as incident medical conditions occurring outside of a Days 1 to Days 15 period following each vaccination and not considered SAEs) will be recorded for all participants at each study visit throughout the study.

Specific procedures to be performed during the study, as well as their prescribed times and associated visit windows, are outlined in the SoA in Section 1.3. Details of each procedure are provided in Section 8.

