1.3 Schedule of Activities

Schedule of Activities for 3-dose in 9 to 15 years old boys (vaccination at Day 1, Month 2 and Month 6)

Study Period	Period I			Period II		Notes	
Visit Number	1	2	3	4	5	6	
Scheduled Day/Month	Day 1	Month 2	Month 6	Month 7	Month 18	Month 30	
Visit Window*		±3 weeks	±4 weeks	3 to 7 weeks after Month 6	±4 weeks	±4 weeks	To calculate visit windows, assume 1 month=30 days and 1 week=7 days
Administrative Procedures							
Obtain Informed Consent/Assent	X						Obtain documented assent from the participant as far as possible
Obtain Informed Consent/Assent for Future Biomedical Research	Х						Participation in future biomedical research is optional and consent must be obtained before collection of blood [deoxyribonucleic acid (DNA)] samples. Obtain documented assent from the participant as far as possible
Review Inclusion/Exclusion Criteria	X						
Assign Participant Identification Card	X						
Collect Medical History	X						
Update Medical History (new conditions not already recorded as medical history or adverse events)		X	X	X	X	X	
Review Prior/Concomitant Medication and Non-study Vaccination	X	X	X	X	X	X	See Section 6.5 for prerequisites for medications and non-study vaccines and Section 8.1.6 for data collection timeframe.
Vaccine Allocation/Randomization	X						

Study Period		Peri	iod I		Peri	od II	Notes
Visit Number	1	2	3	4	5	6	
Scheduled Day/Month	Day 1	Month 2	Month 6	Month 7	Month 18	Month 30	
Visit Window*	-	±3 weeks	±4 weeks	3 to 7 weeks after Month 6	±4 weeks	±4 weeks	To calculate visit windows, assume 1 month=30 days and 1 week=7 days
Clinical and Laboratory Procedures							
Measure Oral Temperature	X	X	X				Prior to each vaccination and Day 1 blood sample collection. Participants who have a fever (defined as an oral temperature of ≥37.5°C) within the 24-hour period prior to vaccination should not receive study vaccine and the vaccination visit must be rescheduled.
Record Height and Weight	X						Prior to vaccination
Physical Examination (optional, per investigator's discretion; perform if needed to assess inclusion/exclusion criteria)	X						
Blood Sample Collection (Serum for anti- HPV)	X			X	X	X	Serum for anti-HPV antibody testing must be collected before vaccination on Day 1
Blood Sample Collection (DNA) for Future Biomedical Research	X						Prior to vaccination from enrolled participants only (optional)
9vHPV Vaccine Administration	X	X	X				

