8.1.4 Medical History

A medical history will be obtained by the investigator. At Visit 1 (Day 1), the participant's medical history for the year prior to Visit 1 will be collected.

After the Day 1 visit, any new medical history that has not been previously documented (ie, incident medical conditions occurring outside of Days 1 to Days 15 period following each vaccination and not considered SAEs) will be collected.

PROTOCOL/AMENDMENT NO.: 066-02

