All participant's legally acceptable representative will be expected to bring the VRC to the study site at the next scheduled visit. The investigator or delegate will review the data captured on the VRC with the participant's legally acceptable representative at Visit 2 (Month 2), Visit 3 (Month 6, only for 3-dose boy arm), and Visit 4 (Month 7). For the AEs outlined above, the investigator will use the information provided by the participant's legally acceptable representative both on the VRC, and verbally at the time of VRC review, to apply the appropriate assessment of causality as described in Appendix 3. At the time of VRC review at the next scheduled visit, participant's legally acceptable representative will be questioned regarding any new medical conditions that occurred beyond Day 15 postvaccination. The investigator will determine if the medical condition is to be reported as an SAE using the reporting guidelines provided in Section 8.4.

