9.6.2 Statistical Methods for Safety Analyses

Safety and tolerability will be assessed by clinical review of all relevant parameters including adverse events (AEs).

The analysis of safety results usually follows a tiered approach in the studies conducted by the Sponsor. However, this study has no comparison between study arms. Thus, the following summaries will be provided as described in Table 8.

- Incidence is defined as (number of participants with the indicated endpoint divided by the total number of participants with follow-up over the relevant period)*100%.

- For the measured adverse events of redness and swelling, 0 to 1 inch will be categorized as mild intensity, >1 inch to 2 inches will be categorized as moderate intensity, and >2 inches will be categorized as severe intensity.

The specific events of interest in this study will be injection-site prompted adverse events on the VRC, such as pain/tenderness, swelling and redness/erythema occurring Day 1 through 5 following any vaccination, and elevated temperature (≥37.5°C), from Day 1 through 5 following any vaccination.

Table 8 Analysis Strategy for Safety Parameters

		Follow-Up	Period	
		After Any	Vaccination Visit	
	Within			
	study			Any Time
	arm	Day 1	Day 1	During
Adverse Event Endpoint	95%CI [∥]	to Day 5 [†]	to Day 15 [†]	Study
Clinical AEs/vaccine-related AEs				
Any AEs/vaccine-related AEs			•	
Deaths				•
Injection-site AEs/vaccine-related AEs				
Injection-site AEs/vaccine-related AEs of pain/tenderness,	•	•		
swelling, and redness/erythema	•	•		
Other injection-site AEs/vaccine-related AEs				
Severe injection-site AEs§/vaccine-related AEs	•	•		
Number (%) of participants by maximum intensity rating,		•		
over all injection-site AEs§/vaccine-related AEs				
Number (%) of participants by maximum intensity rating,		•		
within each of the categories of injection-site AEs [§] /vaccine-related				
AEs				
Systemic AEs/vaccine-related AEs	ı		_	1
Any systemic AEs/vaccine-related AEs	•		•	
Number (%) of participants by maximum intensity rating,			•	
over all systemic AEs/vaccine-related AEs				
Temperatures	ı	1	_	1
Elevated temperatures#	•	•		
Maximum temperatures ^{††}		•		
AEs of Special Interest				
Serious AEs	•		•	•
Serious vaccine-related AEs	•		•	•
New medical conditions ^{‡‡}				•
Pregnancy outcomes				•
Pregnancy outcomes				•

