[†] The day of vaccination is counted as Day 1. Day 1 to Day 5 refers to the period within 4 days of a vaccination. Day 1 to Day 15 refers to the period within 14 days of a vaccination.

For the measured adverse events of redness and swelling 0 to 1 inch will be categorized as mild, >1 inch to 2 inches will be categorized as moderate and >2 inches will be categorized as severe.

[#] Defined as maximum (over the follow-up period) temperature ≥37.5°C.

^{††} Distribution of maximum temperatures over the relevant follow-up period.

^{‡‡} Including new medical conditions considered potentially of an autoimmune nature.

The exact binomial method proposed by Clopper and Pearson (1934).

AEs = Adverse events; CI = Confidence interval

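### Table 8's only row for potentially autoimmune conditions is labelled as covering the whole study, but by definition it leaves out onsets on Days 1–15 after each dose and all serious cases

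*Combined protocol and SAP*

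**What the plan says.** Section 4.1 defines the term: "New medical conditions (defined as incident medical conditions occurring outside of a Days 1 to Days 15 period following each vaccination", with the further condition that the event is not an SAE. Section 8.1.4 repeats it: "incident medical conditions occurring outside of Days 1 to Days 15 period following each vaccination and not considered SAEs".

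Collection follows the definition. Under Section 8.3.4 the representative is "questioned regarding any new medical conditions that occurred beyond Day 15 postvaccination". The Schedule of Activities (Section 1.3) carries the item "Update Medical History (new conditions not already recorded as medical history or adverse events", so a condition already entered as an AE is not entered again.

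In Table 8 (Section 9.6.2), "New medical conditions" stands under the heading for AEs of special interest. It is marked only in the column for any time during the study and has no mark for a confidence interval. Its footnote reads "Including new medical conditions considered potentially of an autoimmune nature" and sets no time limit. Another footnote fixes the length of the post-dose window: "Day 1 to Day 15 refers to the period within 14 days of a vaccination". Section 9 neither repeats nor changes the definition of a new medical condition.

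**The concern.** A reader of the results table will take the row at its label: potentially autoimmune conditions seen at any point in the study. Under the definition it is a count of non-serious conditions with onset outside the two weeks after each dose. For a vaccine given to healthy children, early onsets and serious cases are the ones a safety reader would look for first.

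No other row fills the gap. A non-serious onset on Days 1–15 enters the rows for any AE and any systemic AE, and a reported serious case enters the SAE rows. None of these rows marks an event as potentially autoimmune, and Section 8.4.7 names no events of clinical interest. Section 5.2 excludes children with an autoimmune condition at entry, so a diagnosis during the trial would generally be a new one, which is what this row appears meant to show.

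What is at stake is the conclusion drawn from a zero or a low count in that row.

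**Working it through.** The plan gives no rate, precision or coverage figure for this row, so there is nothing to reproduce. The check is to trace where each kind of case is counted, then count the days left out.

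**Where a potentially autoimmune condition is counted** (Sections 4.1, 8.1.4, 8.4.1 and Table 8)

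| Case | Where it is counted | Identified as potentially autoimmune? |
|---|---|---|
| Non-serious, Days 1–15 after a dose | Any AE; any systemic AE | No |
| Non-serious, any other time | New medical conditions | Yes |
| Serious, from allocation to 6 months after last dose | SAE rows | No |
| Serious, later, vaccine-related or fatal | SAE rows; deaths | No |
| Serious, later, unrelated and non-fatal | SAE report not required; not a new medical condition by definition | No; may be in neither record |

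Only the second line reaches the autoimmune summary.

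**Days left out of the row**

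- Window: vaccination day plus 14 days = 15 days per dose (Table 8 footnote).
- Doses: three in one arm, "3-dose (Day 1, Month 2 and Month 6) in boys aged 9 to 15 years", and two in each of the others (Day 1, Month 6).
- Month length: 30 days (Section 1.3). Period I = 7 × 30 = 210 days; Period II = 23 × 30 = 690 days; whole study = 30 × 30 = 900 days.
- Overlap: the shortest gaps within the visit windows are 60 − 21 = 39 days (doses 1 to 2) and 152 − 81 = 71 days (doses 2 to 3, where 152 = 180 − 28 and 81 = 60 + 21). Both exceed 15, so the windows do not overlap.
- Location: the earliest Month 7 visit is 21 days after the last dose, so every excluded window closes within Period I.

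| | 3-dose arm | 2-dose arms |
|---|---|---|
| Excluded days | 3 × 15 = 45 | 2 × 15 = 30 |
| Share of Period I | 45/210 = 21.4% | 30/210 = 14.3% |
| Share of whole study | 45/900 = 5.0% | 30/900 = 3.3% |
| Days covered, whole study | 855 | 870 |

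Visit windows let Period I run from 180 − 28 + 21 = 173 days to 180 + 28 + 49 = 257 days. The excluded share of Period I then ranges from 26.0% to 17.5% (3-dose) and from 17.3% to 11.7% (2-dose). No Period II time is excluded by the Days 1–15 rule, but the exclusion of SAEs applies there too.

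**What this could do to a reported proportion.** This is illustration only, because the documents give neither an incidence nor an onset pattern. Assume a true 30-month incidence of 3% for non-serious conditions.

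- Constant hazard: 1 − 0.97^(855/900) = 2.85% (3-dose) and 1 − 0.97^(870/900) = 2.90% (2-dose).
- A quarter of onsets on Days 1–15: 3% × 0.75 = 2.25%.
- Half of onsets on Days 1–15: 3% × 0.5 = 1.5%.

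The range is wide because it depends on onset timing, which is unknown. Leaving out serious cases would lower these figures further, by an amount that also cannot be derived.

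**The case against.** The strongest reply is that this is a division between records and not a gap in surveillance. Days 1–15 have the fullest collection in the study: all AEs are reportable, the vaccination report card covers them, and any systemic AE on those days is tabulated with a confidence interval. The term is defined twice, and Table 8 uses the defined term. The row is not among the safety endpoints in Section 3 or Section 9.4.2, so no endpoint estimate is affected. All of this stands. A reader might infer that early autoimmune events go uncollected, or that the primary safety analysis is wrong; the documents support neither.

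A reader might also infer that the row distorts a comparison between regimens, since the excluded time is 45 days in one arm and 30 in the others. Over the whole study that is 855 against 870 covered days, and Section 9.6.2 says that arms are not compared. The arm difference is minor.

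It is equally tempting to treat the row as complete outside the post-dose windows, or to suppose that existing data would support a complete autoimmune count to Month 30. Neither holds. The definition removes SAEs at all times. From 6 months after the last dose (about Month 12), SAE reporting is required only for vaccine-related or fatal events. That leaves 18 months, or 540 of 900 days, in which an unrelated, non-fatal serious case may be in neither record.

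Finally, the plan gives no criteria for calling a condition potentially autoimmune, so extending the classification takes somewhat more than adding a line to a table. That is fair, but the footnote already presupposes such a judgement for this row.

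The replies do not meet the central point: knowing that early-onset and reported serious cases sit somewhere in the general AE and SAE rows does not tell a reader how many of them are potentially autoimmune.

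**Conclusion.** The point holds as a mismatch between label and content in one safety summary. As written, the only autoimmune summary leaves out onsets in 45 days (3-dose) or 30 days (2-dose), all in Period I, and all serious cases throughout. The time lost is small over the study, 5.0% or 3.3%, but it is the time closest to vaccination.

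How far the row would understate the true number of affected participants is unknown. With 100 per arm, each participant missed is 1 percentage point, but the documents give no basis for expecting any particular number.

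The conclusion rests on the definition in Sections 4.1 and 8.1.4 governing Table 8, which nothing in Section 9 contradicts, and on the planned schedule with 30-day months. It is a worthwhile, inexpensive improvement to the safety tables and not a defect in any endpoint.

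**What to change.** Make two changes to Table 8, through the supplemental SAP and before the first database lock, because the girls' base phase is reported first.

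1. Relabel the existing row *New medical conditions (non-serious, onset outside Days 1–15 after each dose)*.
2. Add one row, *Participants with any potentially autoimmune condition recorded as an AE, SAE or new medical condition*, by arm, for Period I and overall. Footnote it to say that SAEs more than 6 months after the last dose are collected only if vaccine-related or fatal, so that the new label does not promise more than its data.

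The cost is one extra row, and applying to AE and SAE terms the same autoimmune classification used for new medical conditions. Since the plan does not give the criteria, they should be written down once and used for all three sources. No new data collection is needed.

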8.4 Adverse Events, Serious Adverse Events, and Other Reportable Safety Events

The definitions of an AE or SAE, as well as the method of recording, evaluating, and assessing causality of AE and SAE and the procedures for completing and transmitting AE, SAE, and other reportable safety event reports can be found in Appendix 3.

Adverse events, SAEs, and other reportable safety events will be reported by the participant (or, when appropriate, by a caregiver, surrogate, or the participant's legally authorized representative).

The investigator and any designees are responsible for detecting, documenting, and reporting events that meet the definition of an AE or SAE as well as other reportable safety events. Investigators remain responsible for following up AEs, SAEs, and other reportable safety events for outcome according to Section 8.4.3.

The investigator, who is a qualified physician, will assess events that meet the definition of an AE or SAE as well as other reportable safety events with respect to seriousness, intensity and causality.

8.4.1 Time Period and Frequency for Collecting AE, SAE, and Other Reportable Safety Event Information

All AEs, SAEs, and other reportable safety events that occur after the participant's legally acceptable representative provides documented informed consent but before allocation/randomization must be reported by the investigator if they cause the participant to be excluded from the study, or are the result of a protocol-specified intervention, including but not limited to washout or discontinuation of usual therapy, diet, placebo, or a procedure.

From the time of allocation/randomization through 14 days following the first vaccination(s) and from the time of any subsequent vaccination(s) through 14 days thereafter, all AEs, SAEs, and other reportable safety events must be reported by the investigator. All SAEs and other reportable safety events that occur from the time of allocation/randomization through 6 months following the last vaccination must be reported by the investigator, regardless of whether the events are considered to be vaccine-related by the investigator.

Additionally, any SAE brought to the attention of an investigator at any time outside of the time period specified in the previous paragraph also must be reported immediately to the Sponsor if the event is either:

- A death that occurs prior to the participant completing the study, but outside the time period specified in the previous paragraph.

OR

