
 An SAE that is considered by an investigator, who is a qualified physician, to be vaccine related.

Investigators are not obligated to actively seek AEs or SAEs or other reportable safety events in former study participants. However, if the investigator learns of any SAE, including a death, at any time after a participant has been discharged from the study, and he/she considers the event to be reasonably related to the study intervention or study participation, the investigator must promptly notify the Sponsor.

All initial and follow-up AEs, SAEs, and other reportable safety events will be recorded and reported to the Sponsor or designee within the time frames as indicated in Table 4.

Table 4 Reporting Time Periods and Time Frames for Adverse Events and Other Reportable Safety Events

Type of Event	Reporting Time Period: Consent to Randomization/ Allocation	Reporting Time Period: Randomization/ Allocation through Protocol-specified Follow-up Period	Reporting Time Period: After the Protocol- specified Follow-up Period	Time Frame to Report Event and Follow-up Information to Sponsor:
NSAE	Report if: - due to protocol- specified intervention - causes exclusion - participant is receiving placebo run- in or other run-in treatment	Report all	Not required	Per data entry guidelines
SAE	Report if: - due to protocol- specified intervention - causes exclusion - participant is receiving placebo run- in or other run-in treatment	Report all	Report if: - drug/vaccine related any death until participant completion of study (Follow ongoing to outcome)	Within 24 hours of learning of event
Pregnancy/ Lactation Exposure	Report if: - participant has been exposed to any protocol-specified intervention (eg, procedure, washout or run-in treatment including placebo run-in)	Report all	Previously reported - Follow to completion/ termination; report outcome	Within 24 hours of learning of event
Cancer	Report if: - due to intervention - causes exclusion	Report all	Not required	Within 5 calendar days of learning of event (unless serious)
Overdose	Report if: - receiving placebo run- in or other run-in medication	Report all	Not required	Within 5 calendar days of learning of event

NSAE=nonserious adverse event; SAE=serious adverse event

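### Sections 4.1 and 8.1.4 exclude SAEs from new medical conditions even after all-cause SAE recording has ended, in conflict with the Schedule of Activities

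*Combined protocol and SAP*

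**What the plan says.** **Definition.** Section 4.1 restricts new medical conditions to those "occurring outside of a Days 1 to Days 15 period following each vaccination and not considered SAEs". Section 8.1.4 glosses new medical history in the same way: "incident medical conditions occurring outside of Days 1 to Days 15 period following each vaccination and not considered SAEs".

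**SAE collection.** Section 4.1 states: "SAEs will be recorded regardless of causality from the time of allocation/randomization through 6 months post last dose". It adds: "Vaccine-related SAEs and deaths will be collected throughout the study". Section 8.4.1 agrees that all SAEs "through 6 months following the last vaccination must be reported by the investigator". For the period after that, Table 4 asks only for events that are "drug/vaccine related any death until participant completion of study".

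**Schedule of Activities.** The medical-history row is marked at Months 2, 6, 7, 18 and 30 in both schedules. For the 3-dose arm it reads "Update Medical History (new conditions not already recorded as medical history or adverse events"; the row for the 2-dose arms has the same content. It does not exclude SAEs as such.

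**Analysis.** Table 8 in Section 9.6.2 summarises new medical conditions over the whole study, with the footnote "Including new medical conditions considered potentially of an autoimmune nature".

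**The concern.** An exclusion is harmless when the excluded event has somewhere else to go. Events in Days 1 to 15 after a vaccination go to the adverse event form. Serious events go to the SAE form, but irrespective of causality only until 6 months after the last dose. After that, a serious, non-fatal event judged unrelated is no longer reportable as an SAE, while Sections 4.1 and 8.1.4 still bar it from the new-medical-conditions record.

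Safety is a primary objective, and Period II is there partly to assess longer-term safety. If the literal wording is followed, the new-medical-conditions summary keeps non-serious conditions and drops serious unrelated ones after about Month 12. The dividing line is a causality judgement made by an open-label investigator. If some sites follow the Schedule of Activities and others the text, the summary mixes two definitions, and a reader of the table could not tell.

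**Working it through.** **Inputs**
- Last dose: Month 6 ± 4 weeks in all arms, with 30 days per month and 7 days per week (Section 1.3). This gives day 180 ± 28, or day 152 to 208.
- All-cause SAE window: 6 months after the last dose, taken as 180 days.
- End of follow-up: Month 30, or day 900. Period II runs from Month 7 (day 210).

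**Length of the affected period**
- The all-cause window closes at day 152 + 180 = 332 to day 208 + 180 = 388, nominally day 360 (Month 12).
- Time left to Month 30: 900 − 388 = 512 to 900 − 332 = 568 days, nominally 540 days (18 months).
- Share of the 30 months: 540/900 = 60%. Share of Period II: 540/(900 − 210) = 540/690 = 78%.
- Participants who stop vaccination early have a longer period. After dose 1 only it is 900 − 180 = 720 days. After Day 1 and Month 2 only it is 900 − (60 + 180) = 660 days.

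**A new condition arising at Month 20, followed through each rule**

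| Event | SAE rules (4.1, 8.4.1, Table 4) | 4.1 and 8.1.4, literal | Schedule of Activities row, Month 30 |
|---|---|---|---|
| Non-serious | not an SAE | recorded | recorded |
| Serious, judged related | recorded | excluded | already recorded |
| Fatal | recorded | excluded | already recorded |
| Serious, non-fatal, judged unrelated | not required | excluded | recorded |

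Only the last row has no destination under the text sections, and only there does the Schedule of Activities give a different answer about whether the event is recorded at all.

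**Number of events (assumed rate)**
- The documents give no background rate. Assume 0.5 to 2 serious, non-fatal, unrelated events per 100 participant-years.
- Exposure with no dropout: 300 × 1.5 years = 450 participant-years.
- Events: 450 × 0.005 = 2.25 to 450 × 0.02 = 9, or 0.75 to 3 per arm of 100.

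**The plan's own figure.** The only stated figure that depends on SAE capture is the bound of <3.0% for zero SAEs among 100 participants (Section 9.9). It reproduces as a one-sided exact bound: 1 − 0.05^(1/100) = 2.95%. This point does not change that arithmetic.

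**The case against.** The strongest reply is that the exclusion only prevents double entry. In Section 8.1.4 it sits inside an explanation of history not yet documented, so an event that was never reportable as an SAE has not been documented and should be entered. Section 8.3.4 similarly asks the investigator to decide whether a new condition is to be reported as an SAE. The Schedule of Activities is operative text: Section 4.1 refers to it for procedures, and Section 8 requires adherence to it. Data entry guidelines, which are not in the documents, may settle the matter in practice.

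Much of this stands. A reader might infer that these events are captured nowhere; the documents do not support that, because the schedule row would pick them up at Months 18 and 30. A reader might also infer that new medical conditions are the only all-cause safety information in Period II, or that the worst cases are lost. Neither holds: deaths from any cause and vaccine-related SAEs are collected to study end, and pregnancies are reportable.

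The reply does not remove the conflict. Section 4.1 has no such lead-in; its definition stands alone. Section 10.3.2 defines an SAE by outcome, without a time or causality limit. Section 8.4.1 calls late serious events SAEs and then makes only deaths and related events reportable, which favours the literal reading. The instruction in Section 8.3.4 belongs to report-card review at Visits 2 to 4, not to Months 18 and 30.

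**Conclusion.** Wrong as written: the rules conflict. On the literal wording of Sections 4.1, 8.1.4 and 8.4.1 with Table 4, serious, non-fatal conditions judged unrelated fall outside both records for about 18 of 30 months. The Schedule of Activities would record them. The documents do not show which rule sites follow, so actual loss of such events is possible but not established.

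The 2 to 9 events are a ceiling at the assumed rates, not an expectation. They require every site to apply the strict wording and no participant to drop out. No figure can be given for autoimmune conditions alone. The conflict itself does not depend on the assumed rate. The consequence is limited to the completeness and consistency of the Table 8 new-medical-conditions summary. Sample size and the immunogenicity analyses are not affected.

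**What to change.** In Sections 4.1 and 8.1.4, replace the clause that excludes events considered SAEs with *and not already reported as an AE or SAE*. This matches the Schedule of Activities, so a serious condition that arises after the all-cause window and is judged unrelated enters the Table 8 new-medical-conditions summary. Carry the same wording into the eCRF entry guidelines. Leave the SAE reporting window unchanged. A seriousness flag on these entries is optional; it would let the summary show them separately.

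The cost is a wording change in two sections and one guideline. No visit or contact is added, because medical history is already updated at Months 18 and 30. The downside is a few more medical-history entries. If the sponsor already intends the Schedule of Activities meaning, the edit only makes that explicit. It is best made before the Period II data are locked, since unrecorded conditions may be hard to recover later.
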